6.7 Safety Evaluations

Only individuals trained by the Principle Investigator ([name].) and Center Director ([name].) will dispense TMS. The licensed physician ([name] or a suitable medically trained stand-in) will closely supervise any medical instability in patients and will specifically be responsible for training and overseeing syncope and seizure management which are not expected given our screening process but are the two primary health risks with TMS treatment.

[name], a board certified physician, will review all questionable screens for MRI and TMS safety and will be physically present (or a reasonable medically trained stand-in) for every TMS session conducted on any participant who indicates greater than minimal risk for experiencing syncope or a seizure in response to TMS.

Only research personnel will have keys and access to the TMS devices.

7 Statistical Plan

All recruitment will be conducted through the University of Pennsylvania, the Veterans Administration Medical Center, and surrounding community to find 80 patients with PTSD or trauma induced MDD and depressive symptoms. It is anticipated that a large portion of individuals will screen fail, withdrawal from participation or have unusable data. Therefore, 80 individuals will be consented/enrolled in this study, to ensure that there are 40 patients who complete the full protocol with usable data. This sample should provide us with adequate data to compare treatment sites relative to one another, since all patients will receive the standard targeting for TMS and also fMRI-guided TMS.

7.1 Primary Endpoint

The primary endpoint of this study will be clinical improvement due to TMS performed at either the standard brain target or the fMRI-guided brain target.

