1.3 Dose Rationale

Several prior studies have safely utilized TMS outside of its FDA-approved protocol, even in substantially larger doses. For instance, in prior studies subjects have received the FDA-approved 3000 rTMS pulses, but done bilaterally instead of unilaterally (6000 total stimulations) every weekday over 4-6 weeks (see Bakker et al., 2015). Similarly, subjects have received 3600 rTMS pulses every weekday over 10 days (see Chistyakov et al., 2015), or 3000 rTMS pulses every weekday over 6 weeks (see O'Reardon et al., 2007). Another study applied the FDA-approved protocol in more than a double-dose, with 6800 stimulations to 1 site every weekday over 7 weeks average participation (Hadley et al., 2013). The present study utilizes many fewer stimulations than these recent/established protocols, with each visit including a maximum of 3700 pulses (including motor threshold determination).

2 Study Objectives

We aim to establish the clinical efficacy of TMS stimulation using targets defined by resting connectivity in patients. We hypothesize that MRI-defined TMS will yield greater reductions in symptoms and greater improvements in quality of life among patients. In addition, we hypothesize that greater resting state connectivity will predict greater reductions in symptoms following TMS.

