2.1 Primary Objective

• To assess and compare the clinical efficacy of rTMS treatments performed at the standard brain target versus an fMRI-guided brain target

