3.1 General Design

TMS will be administered to either the fMRI-guided target or DLPFC in a randomized, single-blind design. 40 patients diagnosed with Post-Traumatic Stress Disorder (PTSD) or trauma induced Major Depressive Disorder (MDD) and symptoms of depression, as determined by meeting the DSM criteria for PTSD or MDD as a primary diagnosis and scoring ≥10 on the PHQ-9, will be recruited for this study. They will be otherwise healthy adults, aged 18-60, with PTSD or trauma induced MDD as primary diagnosis and without current diagnoses of significant, problematic substance use disorders or with present or past diagnoses of psychosis or bipolar illness. All subjects will receive active TMS, so there is no placebo or sham condition. However, the patients will be blinded as to whether their site of stimulation is based on the clinical standardized targeting method or our novel fMRI-guided targeting method. TMS is administered to one of these two sites over a two-week period, and then TMS will be administered to the other site over a subsequent two-week period following a three week wash out period. All subjects will receive TMS to both sites as a part of the study, but the order is randomized and counterbalanced. All participants will be recruited through the community via study advertisements and through the University of Pennsylvania and the VA. Subjects can express interest by contacting the study staff; in most cases, this will serve as the primary method for acquiring contact information. Physician referrals and the use of the Penn Data Analytics Center will also be incorporated as recruitment methods. Section 4.3 further elucidates all recruitment methods. Prior to any study visits, all subjects will be screened in a telephone interview with a trained member of the study staff or via a self-report screening survey. The first study session will consist of a consenting and extended screening visit. The information collected in this initial visit will determine if the subject meets all inclusion criteria. We will also demonstrate TMS to ensure the subject is comfortable with all study procedures. At the second study session, participants will undergo an MRI procedure for 60 minutes. This will be used to generate the TMS targets for the study. Subjects will then return every weekday (5 days per week, minimum of 4 days per week) over two weeks to receive the TMS treatment (10 sessions). These visits will last approximately 60 minutes each. The daily administration of TMS is a necessary component of the study, as it is consistent with the standard operating procedure for FDAapproved clinical TMS. During the 2 weeks of TMS treatment, subjects will undergo the many of the same clinical assessments used during the screening and baseline visits, in order to examine changes in symptoms. Subjects will then spend 3 weeks away from the study team; during the break, there will be two phone/survey visits used as a safety assessment. After this break, subjects will then return every weekday (5 days per week, minimum of 4 days per week) over two weeks to receive the TMS treatment (10 sessions) to the other site examined in the study. Upon completion of the study, scheduled phone and survey visits will take place every 4 weeks (+/-7 days) over the subsequent 6-month period to monitor continued stability of clinical improvement and/or remaining clinical symptoms. Overall, this study consists of 1 consent/screening visit, 1 MRI scan, 20 total visits for TMS treatment, and 8 phone visits.

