4.1 Inclusion Criteria

- 1. 18-60, male or female, any race
- 2. DSM-5 Diagnosis of PTSD or trauma induced MDD
- 3. PHQ-9 Score ≥10
- 4. Capacity to give informed consent and follow study procedures
- 5. English speaking

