7.4.3 Interim Analysis

After the first 12 participants are run for each protocol, the study team will evaluate the overall rate of change in symptoms. If less than one quarter of participants experience at least a 25% reduction in Hamilton Depression scores, the team will consider a change in stimulation protocol or target. Safety and tolerability will also be assessed at this interval and if the team decides that the procedures are safe and appropriate, enrollment will continue up to 60 participants.

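### The stated aim, primary endpoint and power statement rest on improvement attributed to TMS, but with no untreated control the design supports only the between-site difference that the plan's own analysis sections describe

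*Combined protocol and SAP*

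**What the plan says.** Some parts of the protocol are worded as absolute efficacy.

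- Section 2, Study Objectives: "We aim to establish the clinical efficacy of TMS stimulation using targets defined by resting connectivity in patients".
- Section 7.1: the primary endpoint is "clinical improvement due to TMS performed at either the standard brain target or the fMRI-guided brain target". Section 3.2.1 opens in similar terms.
- Section 7.3: the sample size is justified by the number of patients needed for a significant change in symptoms. It uses a Hedges' g of 1.225 for percentage improvement on the Hamilton scale and arrives at 6 patients. No comparator is named.

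Other parts are worded as a comparison.

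- Section 2.1: "To assess and compare the clinical efficacy of rTMS treatments performed at the standard brain target versus an fMRI-guided brain target".
- Section 7.4: the primary analysis is a Site x Time ANOVA.
- Section 7.4.2: the primary endpoint is described as a comparison, with a reference back to the earlier statement. The Study Summary and the opening of section 7 also speak of comparing sites.

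On design, section 3.1 states "All subjects will receive active TMS, so there is no placebo or sham condition" and "All subjects will receive TMS to both sites as a part of the study, but the order is randomized and counterbalanced". The three-week break follows active treatment, and no untreated lead-in is described.

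On the interim look, section 7.4.3 says that after 12 participants for each protocol "the study team will evaluate the overall rate of change in symptoms". The trigger is "If less than one quarter of participants experience at least a 25% reduction in Hamilton Depression scores", and the response is to consider changing the stimulation protocol or target.

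**The concern.** With two active conditions and no untreated one, change from before to after treatment at either site mixes any TMS effect with natural course, expectation and the effect of about 20 treatment visits. Randomised order lets the trial estimate how the sites differ, subject to period and carryover effects. It does not let the trial say how much of the improvement at either site TMS caused.

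Two parts of the plan nevertheless point the reader to that second quantity: the endpoint wording and the power statement. A report that followed 7.1 and 7.3 could present a significant effect of time, with no difference between sites, as efficacy of both targets. A report that followed 7.4.2 would call the same data a null comparison. The plan should not leave that choice open until the results are known.

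The interim check has a related and smaller weakness. It judges an overall rate, although one of the actions it may lead to is a change of target. A pooled rate does not say which target is doing poorly.

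**Working it through.** **1. Reproducing the plan's 6 patients (section 7.3).** Inputs: d = 1.225, power 0.80, alpha 0.05, sidedness not stated. For a one-sample (paired) t-test, power comes from the noncentral t distribution with n - 1 degrees of freedom and noncentrality d√n.

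| Calculation | n | Power |
|---|---|---|
| One-sample t, one-sided | 6 | 0.82 |
| One-sample t, two-sided | 8 | 0.84 (0.67 at n = 6) |
| One-sample normal approximation, two-sided: ((1.960 + 0.842)/1.225)² = 5.23 | 6 | – |
| Two-sample t, one-sided | 10 per arm | 0.84 |
| Two-sample t, two-sided | 12 per arm | 0.82 |

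Only one-sample versions give 6. The arithmetic alone could equally describe a paired between-site difference. It is the wording of 7.3 that makes it a pre-post calculation, because the effect size is percentage improvement and the target is a change in symptoms. No power is stated for the between-site contrast.

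**2. What a pre-post test shows when TMS does nothing.** Assume no TMS effect and natural improvement of δ standard deviations of change (the documents give no value). The chance that a two-sided paired test at 0.05 is significant with 40 evaluable patients (section 4.5) is:

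| δ (assumed) | 0.3 | 0.5 | 0.8 |
|---|---|---|---|
| P(significant) | 0.46 | 0.87 | 0.999 |

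A significant time effect is therefore weak evidence of efficacy.

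**3. What the supported contrast can detect.** With 40 paired patients, two-sided 0.05, 80% power and no carryover, the detectable standardised difference between sites is about 0.455. The effect of 1.225 in 7.3 does not bear on this contrast.

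**4. The interim check.** Read 12 per protocol as 12 patients per first-treated site, 24 in all, treated as independent. The pooled rule then flags if fewer than 6 of 24 respond, since 25% of 24 is 6. The number of responders is the sum of two independent binomials, Bin(12, p₁) + Bin(12, p₂).

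- Assumed true rates of 45% and 10%: P(fewer than 6 of 24) = 0.30, so the weak site goes unflagged about 70% of the time.
- Assumed rates of 60% and 10%: P = 0.07.

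If the same bar were applied to each site (fewer than 3 of 12), a site at 10% would be flagged with probability 0.89 and a site at 45% with probability 0.04. The cost appears when both sites respond equally well:

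| True rate at both sites (assumed) | Pooled rule flags | By-site rule flags at least one |
|---|---|---|
| 35% | 0.10 | 1 - 0.849² = 0.28 |
| 30% | 0.23 | 1 - 0.747² = 0.44 |

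A by-site trigger would trade masking for false alarms.

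**The case against.** The strongest reply is that the comparative reading is already in the plan. The primary objective in 2.1 compares sites, 7.4 makes Site x Time the primary analysis, and 7.4.2 calls the endpoint a comparison. Section 3.2.1 itself goes on to ask whether guided targets do better than standard ones. The absence of sham is disclosed, and the study is labelled Phase 1. All of this stands, and it is why the randomised comparison survives. It does not remove the conflict: 7.4.2 refers back to an endpoint statement that, in 7.1, contains no comparison, and 7.3 offers power for something else.

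Two stronger readings are tempting and are not supported.

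- A reader might infer that, because entry requires "PHQ-9 Score ≥10", regression to the mean alone would carry patients over the interim bar. The documents do not show this. PHQ-9 selects patients at screening, clinical assessments are repeated at a separate baseline visit, and the interim bar is on the Hamilton scale. A fall from the selecting score is not the change the plan measures. Natural course could still contribute, but no rate is given. With 24 patients, the chance of meeting the bar without any TMS effect runs from 0.03 at an assumed responder rate of 10% to 0.58 at 25%.
- A reader might infer that meeting the bar commits the team to continuing with a failing target. It does not. Missing the bar only prompts the team to consider a change, and meeting it rules nothing out. Nor is this the plan's only adaptive element, since 7.4.1 allows randomisation to be suspended to rebalance the groups.

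It is also fair to say that the wording leaves the interim unit unclear, and that the masking figures assume very unequal rates for two sub-regions of the same cortical area.

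**Conclusion.** The concern holds as a conflict between stated claims and design. Sections 2, 3.2.1, 7.1 and 7.3 point to an effect of TMS within each site, which a trial without an untreated control cannot isolate. Sections 2.1, 7.4 and 7.4.2 point to the between-site difference, which it can estimate, provided period and carryover effects are handled. The size of the risk depends on natural improvement, which the documents do not give. At an assumed 0.5 SD of change, an inert treatment would yield a significant pre-post result 87% of the time. The correction is worth making, but it is one of wording and does not undermine the randomised comparison.

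The interim point is secondary. It rests on assumed responder rates, on one reading of the unit, and on a rule that is not binding. The harm would be an uninformative go-ahead, not an inflated type I error. It justifies reporting by site, but not a by-site trigger, which would raise false alarms and would not separate natural course from effect: at a natural-course rate of 25%, a single site would still reach 3 of 12 with probability 0.61.

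**What to change.** 1. In 3.2.1 and 7.1, restate the primary endpoint as the difference between the fMRI-guided and standard sites in symptom change, in line with 7.4 and 7.4.2. The restated endpoint needs a named scale. Section 7.4 names the Hamilton scale, which is not in the list in 6.6, so the two must be reconciled.
2. In section 2, replace *establish* with *compare*, so that the aim agrees with 2.1.
3. Add a sentence that pre-to-post change within a site is descriptive and will not be reported as an effect of TMS. Mark the 6-patient calculation in 7.3 as not bearing on the primary comparison.
4. In 7.4.3, state the unit of the interim count. Report round-1 responder proportions by first-treated site beside the overall rate, as description. Leave the 25% bar on the overall rate.

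The cost is a narrower stated claim. No patients or visits are added. Each by-site interim proportion rests on 12 patients and will be imprecise, and it shows the team outcomes by target partway through the trial, which is a further reason to keep it descriptive.

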7.2 Secondary Endpoints

The secondary endpoint of this study will be the correlation between resting-state connectivity prior to TMS and the degree of clinical change in response to TMS treatment targeting each circuit.

7.3 Sample Size and Power Determination

Using an effect size (Hedge's g) calculated from published work doing theta burst stimulation treatment for MDD to a nearby brain area (dorso-medial prefrontal cortex) in a sample of 87 patients and yielding an effect size of 1.225 (% improvement, Hamilton Depression scale), a priori power analysis (Power 0.80, p-

value 0.05) indicates that we will need at least 6 patients to generate a significant change in symptoms which is well below our planned enrollment.

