Study Duration	8 months (Screening, 9 weeks of treatment visits with a 3-week break, and 6 months of phone/survey follow-up visits)		
Study Center(s)Center for Neuromodulation in Depression and Stress University of Pennsylvania School of Medicine Department of Psychiatry			
Objectives	We aim to compare the efficacy of rTMS treatment to two sub-regions of the Dorsolateral Prefrontal Cortex (DLPFC). We will examine the standard positioning of TMS used in clinical settings compared with TMS using MRI to guide the precise location of stimulation. We hypothesize that fMRI-guided TMS will produce greater benefit to patients with MDD/PTSD than the standard targeting method for TMS.		
Number of Subjects	N=80; n=40		
Main Inclusion and Exclusion Criteria	18-60; inclusive; no TMS contraindications; no medication use that substantially reduces seizure threshold or interferes with fMRI recordings; PTSD diagnosis or trauma induced MDD (SCID interview) and elevated depression (PHQ \ge 10).		
Investigational Product (drug, biologic, device, etc.)	MagVenture devices for rTMS administration include: -MagPro X100* magnetic stimulator -Cool-B65 Butterfly Coil		
Duration of administration (if applicable)	2 sets of 10 consecutive weekdays (at minimum 4 sessions per week with a total of 10 overall sessions per set)		
Reference therapy	N/A		
Statistical Methodology	Clinical outcome will be evaluated on symptom scales in a TMS target x Time ANOVA. Similarly, rate of change (slope) x TMS Target will indicate how rapidly each treatment improves symptoms.		

Safety Evaluations	TMS protocols will be administered by specially-trained staff from the Center or Neuromodulation in Depression and Stress the University of Pennsylvania Department of Psychiatry. All TMS staff will be trained by the PI ([name].) and the Center Director ([name].).		
Data and Safety Monitoring Plan	The PI will be responsible for monitoring the data quality and the ongoing safety of subjects.		

CONFIDENTIAL

BACKGROUND AND STUDY RATIONALE

Introduction

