7.4 Statistical Methods

The primary analysis will be a Site x Time ANOVA on the Hamilton Depression rating scale comparing pretreatment to symptoms immediately following each round of stimulation. This test will be augmented by a Site x Time ANOVA for pre-treatment compared with the 6 month timepoint to explore the degree of maintenance of treatment benefits.

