7.4.2 Efficacy Analysis

Efficacy analyses will focus on comparisons between clinical symptoms at baseline, after the first 2-week treatment period, and at the end of the second 2-week treatment period. As noted above, the primary endpoint of this study will be a comparison focusing on clinical improvement due to TMS performed at either the standard brain target or the fMRI-guided brain target.

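### The only power calculation (section 7.3, n = 6) is for a change in symptoms, so the statement that the sample is adequate to compare the two sites has no quantitative support

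*Combined protocol and SAP*

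**What the plan says.** Section 7.3 holds the only power calculation. It uses a Hedges' g of 1.225 (percentage improvement on the Hamilton scale) from a published study of 87 patients treated with theta-burst stimulation at the dorsomedial prefrontal cortex. With power 0.80 and p-value 0.05 (sidedness not given), it "indicates that we will need at least 6 patients to generate a significant change in symptoms", and it notes that planned enrolment is far larger.

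The trial's question is comparative:

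- Study Summary, Objectives: "We hypothesize that fMRI-guided TMS will produce greater benefit to patients with MDD/PTSD than the standard targeting method for TMS".
- Section 2.1: "To assess and compare the clinical efficacy of rTMS treatments performed at the standard brain target versus an fMRI-guided brain target".
- Section 7.4: "The primary analysis will be a Site x Time ANOVA on the Hamilton Depression rating scale".
- Section 7.4.2: "the primary endpoint of this study will be a comparison focusing on clinical improvement due to TMS", at the standard or the fMRI-guided target.

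The opening paragraph of section 7 plans for 40 completers out of 80 enrolled and says: "This sample should provide us with adequate data to compare treatment sites relative to one another". Its one reason follows: "since all patients will receive the standard targeting for TMS and also fMRI-guided TMS". Section 3.1 describes the design: both conditions are active, there is no sham, order is randomized, and three weeks separate the two treatment periods.

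**The concern.** A test of whether patients improve and a test of whether one active site beats another concern different quantities. Large improvement at both sites is compatible with no difference between them. The effect size in 7.3 is not a contrast between standard and fMRI-guided targeting, so it says nothing about how far the two sites might differ or how variable that difference is.

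Giving both treatments to every patient can improve precision, but it does not supply a target difference or a variance. As the plan stands, nobody can tell in advance what site difference 40 patients could detect, or whether a difference of that size would matter. If the result is null, the plan offers no prior statement of what it could have ruled out. A confidence interval would help, but section 7 does not name one.

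**Working it through.** **1. Reproducing n = 6.** Inputs from 7.3: d = 1.225, power 0.80, alpha 0.05. Sidedness and test are not stated, so each was tried.

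- One-sample or paired, two-sided normal: n = ((1.960 + 0.842)/1.225)² = 5.23, rounded up to **6**.
- One-sample or paired, one-sided t: power 0.822 at n = 6, so **6**.
- One-sample or paired, one-sided normal: 4.12, so 5.
- One-sample or paired, two-sided t: power 0.672 at n = 6, 0.770 at 7 and 0.843 at 8, so 8.
- Two independent groups: 9 or 11 per group (normal, one- or two-sided) and 10 or 12 per group (t), which is 18 to 24 in total.

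So 6 comes out only as a test of change in one set of patients. It is not a miscalculation.

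**2. What 40 evaluable patients give for the site comparison.** The documents give no site difference, SD or correlation, so no required N can be derived. What a fixed 40 can detect does follow. Assumptions: paired t-test on each participant's difference between sites, two-sided 0.05, 80% power, no carry-over.

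- Detectable difference (noncentral t, 39 df): **0.454** SD of the within-participant difference (0.455 with 38 df, allowing a period term).
- Expected 95% CI half-width: t(0.975, 39)/√40 = 2.023/6.325 = **0.320** SD.
- Power at n = 40 for assumed true differences of 0.5, 0.4, 0.3 and 0.2 SD: 0.87, 0.69, 0.46 and 0.23.

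**3. The same difference in SDs of the outcome.** With equal SDs and correlation r between a participant's two site outcomes, SD of the difference = SD × √(2(1 − r)). For assumed r:

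- r = 0.3: 0.454 × 1.183 = 0.54
- r = 0.5: 0.454 × 1.000 = 0.45
- r = 0.7: 0.454 × 0.775 = 0.35

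**4. If only the first period can be used.** Carry-over is a fair question: the break is three weeks, while 7.4 adds a six-month analysis "to explore the degree of maintenance of treatment benefits".

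- 20 versus 20 completers, two-sample t, no baseline adjustment: detectable 0.909 SD of the outcome; half-width t(0.975, 38) × √(2/20) = 2.024 × 0.316 = 0.640 SD.
- This is conservative. Section 7.5 lets completed time-points from non-completers be used. An assumed 25 versus 25 gives 0.81 SD (half-width 0.57).
- Adjusting for baseline also helps. With an assumed pre-post correlation of 0.5 or 0.7, 0.909 × √(1 − r²) gives 0.79 or 0.65 SD at 20 versus 20.

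**The case against.** The best reply is that the two passages make separate claims. Section 7.3 says only that it addresses a change in symptoms. Section 7 does not cite n = 6 and argues from the design. Sections 3.2.1 and 7.1 word the primary endpoint as improvement at either target, which is roughly what 7.3 addresses. The study is also labelled Phase 1.

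Part of this stands. Section 7 does not rest its adequacy claim on n = 6, and 7.3 does not use the term within-patient; that reading is inferred from its wording and from the arithmetic. The reply still leaves the comparison without any figure. Section 3.2.1 itself goes on to state a comparative aim, 7.4.2 calls the endpoint a comparison, and the primary analysis tests Site x Time. A Phase 1 label does not support a statement of adequacy.

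A reader might infer two stronger things, and the documents support neither. One is that 40 patients are too few: they are enough if the true difference is about 0.45 SD of the within-participant difference or more, and nothing in the documents says whether it is. The other is that a carry-over problem would cut the trial to 20 versus 20 and 0.91 SD. That is an unadjusted, completers-only figure, and 7.5 allows more data than that.

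**Conclusion.** The point holds, and the text is wrong as written. The plan's one sample-size calculation is for a different quantity from its primary comparison, and the adequacy sentence in section 7 has no number behind it. It should be fixed, but it is a fault in the stated justification and not evidence of an underpowered trial.

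With 40 evaluable patients the detectable site difference is about 0.45 SD of the within-participant difference (half-width about 0.32 SD). This rests on a paired t-test, two-sided 0.05, 80% power, no carry-over and 40 analysable pairs. The translation to outcome SDs (0.35 to 0.54) rests on assumed correlations of 0.7 to 0.3.

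**What to change.** In 7.3, delete the n = 6 sentence, or label it as a symptom-change calculation that does not address the site comparison. Then state:

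> With 40 evaluable participants, a paired comparison of sites (two-sided 0.05) has 80% power for a between-site difference of about 0.45 SD of the within-participant difference, with expected 95% CI half-width about 0.32 SD, assuming no carry-over.

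This says what 40 can detect and does not by itself justify 40. The sponsor should add why a difference of that size matters, or declare the comparison to be for estimation. The second choice changes the role of the directional hypothesis in the Study Summary.

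- If a first-period fallback is given, label it conservative: about 0.91 SD of the outcome (half-width 0.64) for 20 versus 20 completers without baseline adjustment, and better with non-completers' first-period data or with adjustment.
- Make the adequacy sentence in section 7 refer to this statement, and report the site comparison with its confidence interval.
- Express the difference in points on the primary depression scale once that scale is settled. Sections 7.3 and 7.4 use the Hamilton scale, while the efficacy list in 6.6 has the MADRS and PHQ-9 and no Hamilton scale.

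A separate, minor point: 7.4.3 continues enrolment to as many as 60; the Study Summary and sections 4, 4.5 and 7 give 80 enrolled for 40 usable; 3.1 has 40 recruited. These may count different people, so the plan should say whom each counts.

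Cost: restating 7.3 and section 7 is wording and needs no extra patients, but the stated justification becomes less favourable. Settling the enrolment total may affect how many are recruited.
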